Wear Experience with Daily Disposable Contact Lenses over a Long Day

NCT04535310

Version dated 14Oct2020

Wear Experience with Daily Disposable Contact Lenses over a Long Day

[name], OD MS

The Ohio State University College of Optometry
Innovation in Vision and Eye care Research Group - iVERG
[name]
[name]
[contact]

Purpose

The purpose of this study is to explore the performance of PRECISION1® lenses on long days of lens wear.

Study Overview

This open-label study is of current soft contact lens who wear contact lenses for longer than a typical work day. Participants will be fit into PRECISION1® contact lenses, or may be existing PRECISION1® contact lens wearers. Participants will be assessed after 1-2 weeks of wear with a follow up visit to insure a successful lens fit. Subject will then be sent links to a survey to complete immediately about their current comfort and vision with lens wear and their status with digital device use at 10, 12, 14 and 16 hours of lens wear each night for 1 week. Participants will return for a final follow-up visit including a VAS survey and the CLDEQ8 survey of their lens wear experience.

Background

Soft daily wear contact lenses are used by an estimated 40.9 million adults in the United States.¹ Contact lenses which are worn for daily wear are considered minimal risk by the FDA, and risks to wearers are minimized by proper lens care and hygiene. Daily disposable contact lenses do not require daily cleaning and overnight storage, which improves the required amount of time to care for contact lenses. In addition, daily disposable contact lenses are associated with less lens deposits, which decreases associated comfort issues in lens wearers, including decreasing the risk of triggering Giant papillary conjunctivitis (GPC) and/or ocular allergic responses in patients.² Additionally, daily disposable contact lens wearers are not likely to expose their lenses to water and tend to have better lens hygiene since these lenses do not require daily cleaning. This is reflected in a study which found less superficial punctate staining and symptoms of dryness when comparing daily disposable contact lens wear with planned replacement lenses.³ The subjects in this study will be fit into PRECISION1 daily disposable contact lenses, which are less likely to be associated with the already minimal risks of daily contact lens wear. Because of these benefits of daily disposable lenses, and the accompanying improvement in comfort, it is likely that these lenses will provide long lasting comfort and vision throughout the day. As many people wish to wear their contact lenses to work and then throughout the evening, it is of interest to know how a lens performs over the course of a day into evening.

Key Endpoints:

- Subjective assessment of comfort and vision at time points of extended contact lens wear.
- Visual Analog Scale survey of lens wear symptoms (comfort, dryness, vision)

Study Time Points:

Visit 1 will be conducted to consent the subject and determine eligibility. Consenting will be conducted via phone call and REDCap and will occur before the subject arrives on site if possible. After consenting, the visit will begin with visual acuity and an evaluation of the subject's ocular health will occur to determine eligibility including positively responding to the question, "Do you currently wear contact lenses over a long day?" This will ensure that subjects are able and willing to participate in the study since long contact lens wear will be needed. Subjects will be asked their normal morning time for inserting lenses and evening time for lens removal. Eligible subjects can be habitual wearers of PRECISION1® Contact Lenses or will be fit into PRECISION1® Contact Lenses. Participants will be fit with PRECISION1® Contact Lenses at this visit and will have a fit assessment and over-refraction completed in order to obtain the best fit and vision. Upon successful fit of lenses, subjects will complete an initial survey of lens experience. Lenses will be dispensed to eligible participants and a second visit will be scheduled.

Visit 2: Precision 1 follow-up visit will occur approximately 1 week (± 3 days) following Visit 1. Visual acuity and contact lenses fit assessment and over-refraction will be completed. If changes to the lens are necessary, those changes will be made and an additional follow up visit will be scheduled. Subjects will be asked their normal morning time for inserting lenses and evening time for lens removal. Subjects who are new to PRECISION1® Contact Lenses will be dispensed additional lenses to wear until Visit 3.

Five evening survey days: On the morning of each survey study day, the subject will report their time of lens insertion to study staff or by entering the time in a RedCap survey. Study staff will communicate with participants by sending a link to complete a brief survey at 10, 12, 14 and 16 hours of lens wear that day via REDCap. The surveys will be deployed on 5 days between Visit 2 and Visit 3 that are determined at the time of Visit 2. Every attempt will be made to complete the surveys on business days if possible.

Final visit: The contact lens follow up visit will occur approximately 1 week (± 3 days) following the follow up visit. Subjects will have visual acuity, an assessment of ocular health. Subjects will then complete surveys about their lens wear experience.

Evening Surveys will include 1-10 forced choice grading of comfort and vision.

End of study surveys will include VAS scales assessing:

- Overall Quality of vision
- End of Day Quality of vision
- Overall comfort

End of Day comfort
Overall dryness
End of Day dryness

Recruitment

Potential subjects may see posters placed on bulletin boards at The Ohio State University or local eye care offices, emails to students, faculty and staff at OSU, online or paper ads, or signs on the OSU buses. A search of the electronic medical records of The Ohio State College of Optometry may be done to identify possible subjects who then may be contacted by email or phone with information about the study. Word of mouth referrals by study team members to OSU employees and friends may occur. Emails to alumni of the OSU College of Optometry may be sent for local doctors to notify eligible potential subjects about the study.

Inclusion criteria:

- Ages 18-40
- Subjects must be current spherical contact lens wearers with longs days of lens wear
- Subjects must have 20/25 or better distance visual acuity with current lenses.
- Subjects should have had an eye exam in the past year (self report).
- Good general health (defined by medication use that has not changed within the last month and the absence of medical conditions or treatments that are deemed confounding to the data as determined by the PI).
- Ability to give informed consent.
- Subjects must have a working smart phone and be willing to download an app and/or receive and respond to texts and emails.
- Willing to spend time for the study. Subjects will be required to attend three study visits, wear contact lenses on days between study visits, and must respond to communications on a smart phone on 5 days between visits 2 and 3.
- Either gender.
- Any racial or ethnic origin.

Exclusion criteria:

- No current ocular inflammation or infection as assessed by the study investigator.

Consent and Confidentiality

A team member trained in the consent process will provide the consent document for the potential subject to read and will review the procedures with reference to the consent form. The individual is then provided with time to read the consent form and offered the opportunity to ask questions. The participant is explicitly told that they may stop participation at any time. All subjects will have the capacity to give informed consent. If there is any doubt as to the subject's ability to consent to the study, the subject will be excluded from the study. If the subject agrees to take part in the screening or measurement, he or she will sign and date the most recent IRB-stamped consent as will the team member. The subject will be provided with a copy of the consent form.

The investigator team is trained in privacy issues and will be reminded of the importance of patient privacy prior to study initiation. Potential study participants will contact us after seeing advertisements, emails or hearing about the study by word of mouth, giving them the choice of whether or not they wish to participate in a study for people with dry eyes. Privacy is protected by limiting information related to study recruitment only, and no other personal or medical information that should be private to the patients. The PHI needed is only for the purposes of this study. It is highly unlikely, indeed extremely remote that the dry eye symptoms or signs are related to private or personal information that should or would be preferred to be kept confidential to the patients. Risk factors for dry eye rarely relate to matters or conditions that would be personal to the patient such as personal relationships, behaviors or diseases that one prefers to keep private and confidential.

Statistical Analysis and Power Calculation

This small sample size was chosen for convenience as this study as enrollment for evening participation may be difficult.

Statistical analysis will include descriptive statistics.

Data Management and Security

During the active stages of the study (recruitment to last measurement visit), all paperwork (consents, questionnaires and data forms) for each subject will reside in a subject folder for easy access throughout the study. The folders will reside in the limited-access research area, in a locked file drawer or cupboard. At the completion of the study or disenrollment of a subject the paperwork in the subject's folders will be reorganized into a regulatory binder (consents, W-9s) and a data binder (questionnaire and data forms) and will reside in an office in the limited-access research area. When the data analysis is completed and the study is considered complete, the binders will be stored in the secure Department or Office Clinical Research Area. Paperwork (questionnaire and data forms) for individuals who participate in the baseline visit but are not eligible to continue the study will be stored in the study regulatory binder in an office in the limited-access research area. An electronic file of potential subjects and a file of enrolled subjects with their contact information, as well as electronic files of collected data with the subject number, will reside on a limited-access shared drive with firewall and password protection and is restricted to individuals in the research team. Any electronic data files that contain PHI will be destroyed at the conclusion of the study.

Risks to Subjects and Mitigation

Although rare, a subject could experience eye pain, changes in vision, continued redness or irritation of the eye when inserting or learning to insert a contact lens. More likely transient blurring of vision (less than one minute) or mild, transient (less than a minute) stinging may occur.

Adverse Events

All adverse events will be documented and reported under the guidelines of The Ohio State University Event Reporting guidelines, with any serious, unanticipated and related events being reported to the IRB, by the PI, within 10 days. Adverse Events information will be summarized in the annual report to the IRB at the end of the study. Adverse events will be assessed and determined by [name].

Subject Dismissal

Subjects who, after study team member coaching, are not able to provide analyzable data may be dismissed from the study. Analyzable data is, for example, that which is obtained for the entire measurement interval and provides a readable eye image. Data may not be analyzable if patient isn't able to stand or move freely to utilize the equipment, to name just two causes issues. These issues are usually revealed at the screening assessment visit. Subjects who cannot provide analyzable data will be dismissed for the study. Subjects who do not keep scheduled visits within the required time frame will be dismissed from the study. Study team members will make reasonable efforts to accommodate subjects' schedules.

Protocol Violations, Discontinuation

In the event that a member of the study team or a representative of sponsor becomes aware of a major protocol violation, the IRB shall be notified within 10 working days.

References

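### Eligibility attaches no hours to a long day and survey-day lens removal is not described, so the 14 h and 16 h ratings may describe only those still wearing

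*Combined protocol and SAP*

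**What the plan says.** Three places in the protocol describe who counts as a long-day wearer, and none gives a number of hours.

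- Study Overview describes wearers "who wear contact lenses for longer than a typical work day".
- Inclusion criteria: "Subjects must be current spherical contact lens wearers with longs days of lens wear".
- Study Time Points, Visit 1, requires a yes to the question "Do you currently wear contact lenses over a long day" and comments: "This will ensure that subjects are able and willing to participate in the study since long contact lens wear will be needed".

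Visits 1 and 2 also collect habitual wear times: "Subjects will be asked their normal morning time for inserting lenses and evening time for lens removal". No eligibility, scheduling or analysis rule uses those times.

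On the five survey days, "the subject will report their time of lens insertion to study staff or by entering the time in a RedCap survey", and staff then follow up by "sending a link to complete a brief survey at 10, 12, 14 and 16 hours of lens wear that day via REDCap". On the choice of days: "Every attempt will be made to complete the surveys on business days if possible". The survey content that is described is a 1-10 grade for comfort and for vision, with digital device status added in Study Overview. Neither place mentions when the lenses came out or whether they are still in.

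Key Endpoints lists comfort and vision at the extended-wear time points. Statistical Analysis and Power Calculation commits only to descriptive statistics. The text on non-analyzable data, under Subject Dismissal, is framed around eye images and use of equipment. It does not say how a missing evening rating is treated.

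**The concern.** The survey hours are fixed by time since insertion, but the population is not fixed by hours of wear. A subject with an 11 h day can truthfully answer yes and, keeping habitual hours, has no lens in the eye to rate at 12, 14 or 16 h. The described data would then show a blank, or a grade given after removal, and would not tell lenses out from survey missed.

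Two things are at stake. The summary at 14 or 16 h describes those still wearing and responding, which is legitimate if the number is shown but is not a summary of all enrolled subjects. A reader who compares the 10 h and 16 h summaries may also be comparing different people. If the less comfortable subjects take lenses out sooner, the later ratings look too favourable, and these ratings are central to a study of long days of wear.

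**Working it through.** The plan gives no sample size, variability or expected wear time, so there is no figure of its own to reproduce. The steps below separate what follows from the text from what is assumed.

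**1. Surveys a subject can reach (from the text).** Study Time Points gives 5 survey days and 4 survey hours, so the maximum is 5 × 4 = 20. At habitual hours, the reachable number is 5 × (survey hours at or below usual wear):

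| Usual wear | Reachable surveys |
|---|---|
| under 10 h | 0 |
| 10 to under 12 h | 5 |
| 12 to under 14 h | 10 |
| 14 to under 16 h | 15 |
| 16 h or more | 20 |

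**2. Clock time of the last survey (assumed insertion times).** Insertion at 06:00, 07:00 or 08:00 plus 16 h gives 22:00, 23:00 or 24:00. With business days preferred, some removals for reasons of schedule alone are plausible.

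**3. Share still wearing (assumed).** If daily wear time were normal with SD 1.5 h, the share at hour h would be 1 − Φ((h − mean)/1.5):

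| Mean wear | 10 h | 12 h | 14 h | 16 h |
|---|---|---|---|---|
| 13 h | 98% | 75% | 25% | 2% |
| 14 h | about 100% | 91% | 50% | 9% |
| 15 h | about 100% | 98% | 75% | 25% |
| 16 h | about 100% | about 100% | 91% | 50% |

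The 16 h share runs from 2% to 50% over a 3 h range of assumed means, so the documents do not pin it down.

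**4. Effect on a comparison across hours.** Suppose everyone rates at 10 h and a fraction f rates at 16 h. Let m1 and m0 be the 10 h means of those who do and do not rate at 16 h, D = m1 − m0, and Δ1 the mean fall among the 16 h raters.

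- Mean at 10 h, all subjects: f × m1 + (1 − f) × m0
- Mean at 16 h, those who rate: m1 − Δ1
- Apparent fall = difference of these = Δ1 − (1 − f) × D

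This is algebra and needs no SD or distribution. It fails if some subjects do not rate at 10 h. For an assumed Δ1 of 1 point, the apparent fall is:

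| D | f = 75% | f = 50% | f = 25% |
|---|---|---|---|
| 0 | 1 − 0 = 1.00 | 1 − 0 = 1.00 | 1 − 0 = 1.00 |
| 0.5 | 1 − 0.125 = 0.875 | 1 − 0.25 = 0.75 | 1 − 0.375 = 0.625 |
| 1 | 1 − 0.25 = 0.75 | 1 − 0.50 = 0.50 | 1 − 0.75 = 0.25 |

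A negative D would reverse the sign and make the fall look too large.

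**5. What D = 0 does and does not show.** Let Δ0 be the fall that the others would have had with lenses kept in. The full-group fall is f × Δ1 + (1 − f) × Δ0. Subtracting the apparent fall leaves (1 − f) × (Δ0 − Δ1 + D). At D = 0 the remaining gap is (1 − f) × (Δ0 − Δ1). It is zero only if the two groups would have fallen equally. If comfort drops after 10 h and prompts removal, Δ0 exceeds Δ1. With f = 50% and an assumed excess of 1 point, the gap is 0.50 even though D = 0. The 10 h ratings can estimate D but say nothing about Δ0. That is why the reason for removal matters.

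**The case against.** The strongest reply has four parts.

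- **The Visit 1 sentence is modest.** It says the question secures subjects who are able and willing to take part. A reader might infer that the protocol promises 14 to 16 h of wear from every subject; it does not say so. This part stands. The point is only that no hours are attached.
- **Wear span is known to staff.** Habitual insertion and removal times are asked twice, and the survey days are settled at Visit 2. This stands as far as it goes, and the fix uses those times. But no rule draws on them, and a usual removal time is not the actual one on a survey day.
- **Some material cannot be seen.** The full survey form and the consent pages are not shown, and the listed content is visibly partial. A removal item may exist, and subjects may have been told what hours were expected. A reader might infer that removal time is not collected; the documents support only that it is not described.
- **The plan names no hourly mean, fall or trend, and tests nothing.** This stands too. The Background does express interest in performance from day into evening, so a reading across hours is likely, but the plan does not commit to one.

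Every size in the working other than the survey counts is assumed, so the tables show how the mechanism operates and give no estimate for this study.

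**Conclusion.** The point holds as a minor one. As described, the plan allows the 14 h and 16 h summaries to rest on a self-selected subset, and it gives no means of separating lenses out from survey missed. Two stronger conclusions might be drawn, and neither is supported.

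- **That the late ratings are biased.** The documents do not show how many subjects stop early or why. If removal is purely a matter of schedule and unrelated to comfort or its course, there is no bias.
- **That equal 10 h comfort in the two groups would clear the late ratings.** It removes only the composition difference (1 − f) × D and leaves open a later fall that prompts removal.

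The illustrated distortion, 0 to 0.75 of an assumed 1-point fall, rests on assumed f and D of zero or more, with everyone rating at 10 h. Severity stays minor because the study is exploratory, open-label and descriptive, and the consequence is confined to how the later ratings are read.

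**What to change.** 1. Add to the survey-day REDCap form, unless already there: whether the lenses are still in, the time of removal, and the reason.
2. At each survey hour, report the number who rated beside the number whose habitual wear, from the times asked at Visits 1 and 2, reaches that hour.
3. Add the change from 10 h to each later hour, paired within the same day and then averaged within subject. State that it describes only those who wear that long.

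Items 2 and 3 need no new data. No minimum wear time is proposed. The cost is one short item on 5 days and a little more descriptive analysis. The paired change may rest on few subjects at 16 h, given a small convenience sample, and it misses comfort that falls only just before removal. The reason item in step 1 is there to cover that gap.

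### At the final visit the VAS, a key endpoint, is completed after the acuity test and eye examination with no stated safeguard; the effect may be small, and reversing the order costs nothing

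*Combined protocol and SAP*

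**What the plan says.** The final-visit paragraph under Study Time Points sets a sequence: "Subjects will have visual acuity, an assessment of ocular health. Subjects will then complete surveys about their lens wear experience". It does not name the surveys. The Study Overview does: "Participants will return for a final follow-up visit including a VAS survey and the CLDEQ8 survey of their lens wear experience". The survey list that follows the visit descriptions agrees on timing ("End of study surveys will include VAS scales assessing") and gives six scales: vision, comfort and dryness, each rated overall and for the end of the day.

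Key Endpoints has two entries. The first is the subjective rating of comfort and vision at the extended-wear time points. The second is the "Visual Analog Scale survey of lens wear symptoms (comfort, dryness, vision". The CLDEQ8 is not listed there.

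The study is open-label, every participant wears the same lens, and no comparator is described. Under Statistical Analysis and Power Calculation the analysis is descriptive, and the sample size is explained only as a matter of convenience: "This small sample size was chosen for convenience as this study as enrollment for evening participation may be difficult". No number of subjects is given.

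**The concern.** A self-rated endpoint is best collected before anything at the visit can influence the answer. Here the subject reads an acuity chart and then rates quality of vision, and has the eyes examined and then rates comfort and dryness. The VAS is meant to summarise wear over the preceding days, so taking it after the examination adds nothing to the measurement and may add something unwanted.

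The design gives little protection if a shift occurs. Subject and staff know the lens, everyone follows the same order, and the descriptive summary of the final-visit ratings is itself the result. A shift caused by the visit would be reported as lens performance.

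**Working it through.** No figure in the plan depends on survey order, so there is nothing to reproduce. The check sets the relevant sections side by side.

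**1. Is the order really stated?** Yes. The final-visit paragraph puts the surveys after acuity and the eye assessment. The Study Overview names the surveys without placing them relative to the examination, so it does not contradict this. No section puts the surveys first, holds findings back until they are complete, or says what the ocular health assessment consists of.

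**2. Which items could be reached, and by what route?** Three domains times two time frames gives 3 × 2 = 6 VAS items.

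| Items | Acuity test just taken | Examination or remarks | Parallel in the evening surveys |
|---|---|---|---|
| Vision (2) | Yes, directly | Possible, undocumented | Yes |
| Comfort (2) | No | Possible, undocumented | Yes |
| Dryness (2) | No | Possible, undocumented | None |

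The documented route, the acuity test, reaches 2 of 6 items. The other 4 depend on an assumption about the examination.

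**3. What is unaffected?** The evening ratings are collected remotely, by "sending a link to complete a brief survey at 10, 12, 14 and 16 hours of lens wear that day via REDCap". Under Study Time Points this happens on five days, so up to 4 × 5 = 20 ratings per subject for each of comfort and vision, all completed before the final visit. They use a 1-10 forced-choice grade rather than a VAS, so they can show whether the VAS points the same way but cannot calibrate its level. They do not ask about dryness. The CLDEQ8 is taken at the same visit in the same position, so it is no independent check.

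**4. What would a shift do?** Let μ be the mean an item would have without the visit's influence, and δ the average shift the visit causes. The reported mean then estimates μ + δ. With two arms in the same order, a common δ would cancel: (μA + δ) − (μB + δ) = μA − μB. With one group it stays, and because the number of subjects does not enter, a larger sample would not reduce it. The documents give no δ, no standard deviation and no sample size, so neither the size nor the sign of δ can be derived.

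**5. What about Visit 1?** The first survey also follows acuity, an ocular health evaluation and lens fitting: "Upon successful fit of lenses, subjects will complete an initial survey of lens experience". If its shift is δ1 and the final-visit shift is δ2, an initial-to-final difference estimates the true change plus (δ2 − δ1). Under the present order the two may partly cancel. With surveys first at the final visit, δ2 is close to zero and −δ1 remains. The fix therefore protects the final-visit level but could add an order difference to a comparison across visits. The documents plan no such comparison and do not say that the initial survey uses the same scales.

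**The case against.** The strongest reply is that the influence is speculative and the consequence slight. The items ask for overall and end-of-day experience, not how the eye feels in the clinic, so a brief examination may hardly move them. The acuity chart offers little news: subjects need 20/25 or better with their current lenses to enter and have acuity measured at Visits 1 and 2. Nothing in the protocol describes bright light, handling of the eye or comments to the subject. The first-listed key endpoint bears directly on the study's purpose and is untouched. The analysis is descriptive, so no test or threshold turns on a VAS mean.

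Most of this stands, and it limits the weight of the point. It does not remove it. A recalled rating can still be coloured by what the subject has just experienced or been told, no safeguard is stated, and the plan gives no reason for the present order. Dryness is covered by no other key endpoint.

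A reader might go further and infer that all six items are shown to be biased and that nothing in the design offsets it. The documents do not support that. Only the two vision items have a documented route, and the evening ratings give a partial check on comfort and vision.

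**Conclusion.** The point holds in a limited form. The stated order exposes a key endpoint, and the CLDEQ8 with it, to an avoidable influence. For the two vision items this rests on the plan's own sequence. For the four comfort and dryness items it rests on the assumption that the examination, or remarks made during it, can affect the answer. Whether any shift occurs, in which direction and by how much cannot be determined from the documents; it may be small.

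It would be wrong to conclude that the VAS results are unusable, or to attach a number of scale points to the effect, since any such number would be invented. This is a free improvement of optional to moderate priority. It matters most for dryness, which has no parallel in the evening surveys.

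**What to change.** Replace the order in the final-visit paragraph of Study Time Points with: *On arrival at the final visit, before visual acuity, any examination or any discussion of findings, subjects complete the VAS and CLDEQ8 surveys; visual acuity and the assessment of ocular health follow.*

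If the initial survey is ever compared with the final one, the report should state that the initial survey followed acuity, ocular health evaluation and fitting while the final one preceded the examination.

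The cost is one sentence of protocol text. The surveys, staff, visit length and sample size do not change, and the eye assessment is still done in full.

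### Wear hours run from one morning insertion time, and no survey-day item is described on whether that lens is still in, replaced or removed, or on drops, so late ratings cannot be tied to 10–16 hours on one lens.

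*Combined protocol and SAP*

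**What the plan says.** The first item under Key Endpoints is "Subjective assessment of comfort and vision at time points of extended contact lens wear". Elapsed wear is therefore the axis on which this endpoint is read.

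Under Study Time Points, the paragraph on the five evening survey days sets the clock: "On the morning of each survey study day, the subject will report their time of lens insertion to study staff", or enters it in REDCap. Staff then prompt the subject by "sending a link to complete a brief survey at 10, 12, 14 and 16 hours of lens wear that day via REDCap".

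Survey content appears in two places. The list of survey items that follows Study Time Points says "Evening Surveys will include 1-10 forced choice grading of comfort and vision". The Study Overview describes the same survey as covering "current comfort and vision with lens wear and their status with digital device use at 10, 12, 14 and 16 hours".

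On lens removal, Visits 1 and 2 each carry the sentence "Subjects will be asked their normal morning time for inserting lenses and evening time for lens removal". That records habit, not what happened on a given survey day.

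On supply, lenses are dispensed at Visit 1, and Visit 2 adds: "Subjects who are new to PRECISION1® Contact Lenses will be dispensed additional lenses to wear until Visit 3". No quantity is given. Drops are not mentioned anywhere, whether as allowed, barred or recorded. The Statistical Analysis section plans descriptive statistics only and has no rule for ratings given after a lens change, a removal or drops.

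**The concern.** The lens is a daily disposable, and subjects have a supply at home. They are chosen because they already wear lenses over long days, and they know that long wear is needed for the study. Someone who is uncomfortable in the evening could put in a fresh lens, use drops or take the lens out before a survey arrives. As described, the data would record each of these ratings in the same way as a rating of the morning lens worn without interruption.

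At stake is the reading of the 14 and 16 hour ratings, which matter most to a study of long days. The study is open-label with no comparator described, so no control group would share and offset the effect. If the subjects who act are those whose comfort or vision is falling, the likely error runs in the direction that the Background section already expects, namely good performance late in the day. This information has to be collected at the time, because later analysis cannot reliably recover it.

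**Working it through.** The documents state no figure on this point, so there is nothing to reproduce. The check has three parts.

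**1. What is described as collected, against what is needed to tie a rating to hours on one lens**

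| Needed on a survey day | Described in the protocol? |
|---|---|
| Time the morning lens went in | Yes, self-reported (five evening survey days) |
| Whether that lens is still in at the survey | No |
| Time of any replacement | No |
| Time of any removal | No; only the usual removal time, at Visits 1 and 2 |
| Drops since insertion or since the last survey | No |

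The end-of-study visual analogue items cover vision, comfort and dryness. The Study Overview adds the CLDEQ8 at the final visit. A single questionnaire at the end cannot identify which hourly rating followed drops or a change.

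**2. Effect on the wear-time label**

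For a replaced lens, true lens age = nominal hour − hour of replacement. Take insertion at 07:00 and a fresh lens at 17:00, that is, at hour 10, just after the first survey (assumed clock times):

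| Survey clock time | Nominal hour | Age of lens being rated |
|---|---|---|
| 17:00 | 10 | 10 h (before the change) |
| 19:00 | 12 | 12 − 10 = 2 h |
| 21:00 | 14 | 14 − 10 = 4 h |
| 23:00 | 16 | 16 − 10 = 6 h |

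Three of that day's four ratings carry the wrong lens age. The count depends on timing: a change before hour 10 would affect all four.

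The other two actions work differently. After drops, the lens age is right, but the rating describes an eye that has been relieved. After removal, the rating describes no lens.

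**3. Possible effect on a late-hour mean**

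Shift in the mean = f × u, where f is the share of ratings at that hour given after drops or a fresh lens, and u is the resulting rise on the 1–10 scale. Neither is in the documents. On purely assumed ranges of f = 10% to 30% and u = 1 to 3 points:

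- low end: 0.10 × 1 = 0.1 points
- high end: 0.30 × 3 = 0.9 points

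If such use grows through the evening, the fall from 10 to 16 hours would be understated by up to that amount. This shows how the shift scales with the assumptions. It does not estimate what will happen in this study.

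**The case against.** Several points on the other side stand.

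- **The form is not shown.** A reader might infer that nothing at all is collected on drops or lens changes. The documents do not support that. The survey list says what the surveys will include, which is not exhaustive; the Study Overview adds an item that the list omits. What can be said is that no such item is described.
- **Lens in place.** A reader might also assume that every subject is still wearing a lens at every survey. No passage says so, and on a 07:00 insertion the last survey falls at 23:00. Removal therefore belongs in the point.
- **Spare lenses.** The text says additional lenses are dispensed to new wearers. It does not say how many, so a spare on any given evening is plausible but not documented.
- **Bias.** A reader might conclude that the endpoint is biased. No frequency is given, and it is plausible but not documented that the less comfortable subjects act more often. The documents support only a possible bias of unknown size.
- **Drops.** They do not mislabel lens age. If the aim is experience under usual behaviour, which suits an exploratory, descriptive study, ratings after drops are a legitimate result. The concern is stronger for a replaced lens, because the Background section asks how a lens performs across the day into the evening.
- **Subsetting.** Restricting to same-lens, no-drop responses could worsen matters, because it would remove the subjects whose comfort is falling.

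These points narrow the claim and shape the fix. They do not supply the missing link between a late rating and the lens being rated.

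**Conclusion.** The point holds as a gap in described measurement. Wear hours rest on one self-reported insertion time, and nothing described would show whether a rating at 10, 12, 14 or 16 hours refers to the morning lens, a newer lens, a relieved eye or no lens. In the worked example, one lens change puts 3 of the day's 4 ratings at the wrong lens age, by 10 hours each.

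Late ratings could look better than continuous wear of one lens would give. That direction assumes that changes and drops follow falling comfort. The effect on the means is unknown because the documents give neither the frequency nor the size of any relief. The change is worth making because it is cheap and the information has to be captured on the day.

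**What to change.** Add two items to each evening REDCap survey:

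1. *Are you wearing the same lenses you put in this morning?* Options: same, replaced, removed; with the time of any replacement or removal.
2. *Have you used eye drops since the last survey (or, at the first survey, since insertion)?* Yes or no.

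In the analysis section, state that:

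- all-response ratings by nominal hour are the main display;
- the shares of survey days with replacement, removal and drops are each reported as a performance outcome;
- ratings are also tabulated by status, with replaced lenses shown additionally by age of the current lens;
- the same-lens, no-drop subset is not the main result, because it selects the more comfortable wearers.

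If the form already holds such items, the protocol need only describe them and the tabulation.

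The cost is a few seconds per survey and some extra descriptive tables. With a small convenience sample, the late-hour subgroups may be too thin to interpret. The change only records behaviour; it proposes no rule on whether drops, replacement or removal are permitted.
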